- (H1b) Participants who receive MTcap will use less hypnotic medication post-treatment and at 6 months follow-up compared with those who receive SGT+CBTI: Two outcomes will be assessed: frequency (i.e., 0 to 7 days used) and quantity (i.e., average daily dose in diazepam milligram equivalents). For each outcome, we will fit a 2 (group) by 3 (time) general linear mixed model. Interaction terms will be used to assess the change in the outcome (baseline→post-treatment, baseline→6 months) for MTcap vs. SGT+CBTI. Power Analysis: We use statistics from our recent study, which found a baseline to 6-month correlation of *r*=0.83 (95% Cl=0.77-0.88) and a standard deviation (SD) of 1.94 for a similar outcome measure—"days used of medications commonly used for insomnia" (0 to 7 days used). Assuming r=0.83 and n=57 per group, we could detect a treatment effect of 0.60 (Cohen's *d*=0.30) (i.e. a difference of 6/10ths of a day between the groups). Assuming *r*=0.77 (i.e., using the LCL), we could detect a treatment effect of 0.70 days (Cohen's *d*=0.36). If we disregard data from our recent study, power calculations still show that we could detect a treatment effect of 1.02 days (Cohen's *d*=.53; i.e., detect a difference of 1 day between groups). For quantity of use, power calculations indicate that we could detect a treatment effect of *d*=.53 (medium effect).
- (H2) Participants who receive MTcap will have lower Insomnia Severity Index scores at 6 months follow-up compared to SGT+CBTI: We will fit a general linear mixed model, and an interaction term will assess the change in ISI from baseline to 6 months for MTcap vs. SGT+CBTI. Power Analysis: Our prior research shows an ISI SD=5.3 and *r*=0.39 (95% CI=0.24-0.52) between baseline ISI and 6 month follow-up ISI. Assuming this correlation and a sample size of N=57 per group, the study could detect an effect as small as 3.1 units on the ISI (or a Cohen's *d*=.58). Assuming *r*=0.24 (i.e., using the LCL), we could detect an effect as small as 3.43 units on the ISI (or a Cohen's *d*=.65). An effect of 4.0 units on the ISI has been

- determined to be clinically-meaningful in prior research, 103 which means that the proposed study would be able to detect effects that are clinically-meaningful (as well as effects that smaller than clinically-meaningful); both of these power analyses suggest that the study could detect effects that are between medium and large effects.

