- (H3) Dysfunctional Beliefs and Attitudes About Sleep (DBAS) Medication Scale ratings will improve compared to SGT+CBTI post-treatment and at 6 months follow-up: We will fit a 2 (group) by 3 (time) general linear mixed model. Interaction terms will be used to assess the change in DBAS medication items (baseline→post-treatment, baseline→6 months) for MTcap vs. SGT+CBTI group. Power Analysis: Our prior research shows a DBAS-16 SD= 2.1 and *r*=0.55 (95% CI=0.39,0.64) between baseline DBAS and 6-month follow-up DBAS. Assuming this correlation and a sample size of N=57 per group, the study could detect an effect size of *d*=0.50, which is a difference of 1.1 units on the DBAS-16. Assuming *r*=0.39 (the LCL), we could detect an effect size of *d*=.58, corresponding to a 1.2 unit change.

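### H1b's fallback detectable difference (1.02 days, d=.53) is a follow-up-only figure and does not describe the planned change-from-baseline interaction

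*Combined protocol and SAP*

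**What the plan says.** All places are in the combined protocol and SAP.

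- **Planned test, Primary Analysis Plan (H1b).** Nights used (0 to 7) and average daily dose are each fitted with a group by three-time-point mixed model. "Interaction terms will be used to assess the change in the outcome" from baseline to post-treatment and from baseline to 6 months.
- **Power with the borrowed correlation.** The recent study gave r=0.83 (lower limit 0.77) "and a standard deviation (SD) of 1.94 for a similar outcome measure". At r=0.83 and 57 per group, "we could detect a treatment effect of 0.60" days; at r=0.77 the figure is 0.70 days.
- **Fallback.** "If we disregard data from our recent study, power calculations still show that we could detect a treatment effect of 1.02 days", given as d=.53. No correlation, SD or design is stated for it. The quantity outcome also gets d=.53 with no correlation.
- **H2.** The test is of the same kind: "an interaction term will assess the change in ISI from baseline to 6 months". At r=0.39, "the study could detect an effect as small as 3.1 units on the ISI" (d=.58); at r=0.24, "we could detect an effect as small as 3.43 units on the ISI" (d=.65).
- **H3.** At r=0.55 the plan gives d=0.50, "which is a difference of 1.1 units on the DBAS-16", and d=.58 at r=0.39.
- **H4, Secondary Analysis Plan.** The outcomes are to be analysed by mixed model as in H3, but the zero-correlation effect size, d=0.52, is labelled as coming from a post-test only analysis.

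**The concern.** The fallback is the figure a reader relies on if the recent study's correlation does not carry over. It reads as the planned test's sensitivity without that study. Yet the plan's own H2 line needs d=.58 to .65 for the same kind of contrast at the same 57 per group when r is 0.39 to 0.24. A smaller d=.53 therefore cannot be free of a correlation assumption if it refers to the interaction. Either a correlation is hidden in it or it belongs to another analysis. H1b is part of Aim 1, a primary aim, so its stated power should match its stated test.

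**Working it through.** **Inputs.** Two-sided alpha 0.05, power 0.80 and 57 per arm (Primary Analysis Plan, opening paragraph); SD 1.94 and r=0.83 or 0.77 (H1b); SD 5.3 and r=0.39 or 0.24 (H2); SD 2.1 and r=0.55 or 0.39 (H3). The values r=0 and r=0.3 are illustrative assumptions.

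**Multiplier.** For two groups of 57, the detectable standardized difference is (1.960 + 0.842) x sqrt(2/57) = 0.525 by the normal approximation, or 0.529 with the t distribution.

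**Formulas**, with the same SD at both times:
- follow-up values only: 0.529 x SD
- change from baseline: 0.529 x SD x sqrt(2(1-r))
- follow-up adjusted for baseline: 0.529 x SD x sqrt(1-r²)

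With complete data, and group means left free at baseline, the interaction in the planned model is the change-from-baseline comparison.

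**Step 1: reproduce the plan's figures with the change formula** (normal to t multiplier).
- H1b, r=0.83: sqrt(0.34) = 0.583, giving 0.594 to 0.599 days (plan: 0.60).
- H1b, r=0.77: sqrt(0.46) = 0.678, giving 0.690 to 0.696 days (plan: 0.70).
- H2, r=0.39: 3.07 to 3.10 units (plan: 3.1). At r=0.24: 3.43 to 3.46 units (plan: 3.43).
- H3, r=0.55: d=0.50 (plan: 0.50). At r=0.39: d=0.58 (plan: .58).

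So the plan uses the change-score formula wherever it states a correlation.

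**Step 2: reproduce the fallback.** Follow-up only: 0.525 x 1.94 = 1.018 days, or 0.529 x 1.94 = 1.027. This matches 1.02 days and d=.53. It also uses the SD of the study the sentence sets aside.

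**Step 3: find the correlation at which the fallback fits the planned contrast.** Solve 0.53 = multiplier x sqrt(2(1-r)): r = 1 - (0.53/0.525)²/2 = 0.49, or 0.50 with 0.529. No such value is stated.

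**Step 4: compare the planned and baseline-adjusted analyses** (SD 1.94 at both times, 57 per arm, t-based).

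| r | Change: detectable days (d) | Change: power for 1.02 days | Adjusted: detectable days | Adjusted: power for 1.02 days |
|---|---|---|---|---|
| 0 | 1.45 (0.75) | 50% | 1.03 | 79% |
| 0.3 | 1.22 (0.63) | 65% | 0.98 | 83% |
| 0.39 | 1.13 (0.58) | 71% | 0.95 | 86% |
| 0.50 | 1.03 (0.53) | 80% | 0.89 | 89% |
| 0.83 | 0.60 (0.31) | over 99% | 0.57 | over 99% |

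Simulation with 20,000 trials per value agrees: change against adjusted, 50% and 79% at r=0, 72% and 85% at r=0.39, 80% and 89% at r=0.50.

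**Step 5: dependence on the SD.** The adjusted figure in days scales with the follow-up SD. If that were 2.5 (an assumption), the r=0 figure would be 0.529 x 2.5 = 1.32 days. With unequal SDs, the change contrast matches the follow-up-only figure at r = baseline SD / (2 x follow-up SD). For assumed SDs of 1.5 and 1.94 that is 1.5/3.88 = 0.39, not 0.50.

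**The case against.** The best defence is that 1.02 days is correct arithmetic for a follow-up-only comparison, that H4 names that approach openly, and that such a comparison is a reasonable conservative benchmark. This stands as far as it goes: there is no calculation error. But the H1b sentence does not name the design, and the planned interaction can do worse than the benchmark.

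Three stronger readings are tempting, and the documents do not support them.

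- **The 0.60 and 0.70 day figures are wrong.** They are arithmetically right, the measure is described as similar rather than identical, and both are stated as conditional on r. One may only note that r=0.83 or 0.77 may not carry over to a taper trial in which H1a works from 59% to 63% discontinuation among controls. The documents give no baseline distribution of nights and no account of who quits, so they cannot show what r will be.
- **The covariate list has a gap because it omits baseline nights and dose.** Baseline is already a time point in the model. Adding it as a covariate to that same model would be a mistake. The choice is between two analyses.
- **Baseline adjustment secures 1.02 days whatever the correlation.** That holds only if the follow-up SD is 1.94, which is as borrowed as the correlation.

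It is also fair to say that adjustment gains little when r is high or when baseline use varies little.

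**Conclusion.** The point holds as a mismatch between a stated power figure and the stated test. The H1b fallback describes a follow-up-only comparison. For the planned interaction, 80% power for 1.02 days requires r of at least about 0.50; below that, power falls, to about half at r=0. These results assume equal SDs at both times (1.94 for the figures in days), 57 per arm and complete data. They do not show that the trial is underpowered for H1b, because the true correlation is unknown and could be high. The quantity outcome has the same mismatch. H4 has it in milder form, since its design is labelled; there d=0.52 would fit the change contrast only at r of about 0.51 to 0.52. The sample size is not affected. The analysis and its power statement should be reconciled before unblinded analysis.

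**What to change.** 1. **Analysis.** For nights and dose, analyse each follow-up value with its baseline value as a covariate, or keep the planned mixed model and constrain baseline means to be equal across arms. Do not do both in one model.
2. **Power statement.** Choose one of two routes. Keep 1.02 days and d=.53 as the r=0 figure for the baseline-adjusted analysis, saying that the days figure depends on a follow-up SD of 1.94 from the prior study and rises with a larger SD. Or restate the fallback for the change interaction with its r and SD, for example 1.45 days (d=0.75) at r=0 and 1.22 days (d=0.63) at r=0.3.
3. **Quantity and H4.** Apply the same choice to d=.53 for quantity and d=0.52 for H4.
4. **0.60 and 0.70 days.** Leave them, with a sentence noting that the correlation comes from another study and may be lower under tapering.

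The cost is SAP wording and about one degree of freedom. Baseline use is already collected (Table 2, medication log), so no further data or participants are needed.

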# Primary Analysis Plan

We plan to randomize 132 individuals, of whom we expect 13% to drop out (i.e., fail to complete assessments) by 6-months, yielding N=114 participants with complete data ( $\sim$  57 per group). We base this drop-out on our completed study ([name] VA Merit 08-295). We will include terms for stratification characteristics and covariates for baseline pain intensity, PHQ-9, and opioid use in all of the models. All analyses below assume  $\alpha$ =0.05, power=0.80, two-sided hypothesis tests, and intention-to-treat approach. Effect sizes are in the measure's natural units and Cohen's d (large=.8; medium=.5; small=.2).

- (H1a) Participants who receive MTcap will have increased likelihood of hypnotic discontinuation post-treatment and at 6 months follow-up compared with those who receive SGT+CBTI: Hypnotic discontinuation (yes=1/no=0) will be regressed on treatment group assignment (MTcap vs. SGT+CBTI) in two logistic regression models (post-treatment and 6 months follow-up). Sample size calculations establish that 114 participants will be adequate to detect a difference of 21% to 26% between the MTcap and SGT+CBTI groups, depending upon the discontinuation percentage of the SGT+CBTI group (59% to 63% at follow-up in prior studies). In our feasibility study, 100% discontinued hypnotics post-treatment. We will use multiple imputation.

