# Secondary Analysis Plan (H4)

[figure not shown]
We will test whether MTcap improves cognition (DSS, Symbol Copy; Trails A & B) and balance (One-leg balance) at post-treatment and 6-month follow-up, using general linear mixed model (see Hypothesis 3 above). Effect size calculations: For the most pessimistic case—no correlation between these measures at the two time points—a post-test only analysis could detect a difference of *d*=0.52.

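### H2's group-by-time test gives up precision that baseline adjustment would recover, and H4's worst-case d=0.52 belongs to a different analysis from the one specified

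*Combined protocol and SAP*

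**What the plan says.** The Primary Analysis Plan expects 132 randomised (66 per arm) and about 57 completers per arm. It uses two-sided alpha 0.05 and 80% power. Every model includes the stratification terms and "covariates for baseline pain intensity, PHQ-9, and opioid use in all of the models". The baseline value of the outcome is not listed.

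- **H2.** In a general linear mixed model, "an interaction term will assess the change in ISI from baseline to 6 months for MTcap vs. SGT+CBTI". With SD 5.3 and a baseline to 6-month correlation r=0.39 (95% CI 0.24–0.52), "the study could detect an effect as small as 3.1 units on the ISI". At r=0.24 the figure is 3.43. The benchmark for clinical meaning is 4.0 units.
- **H3.** In a two-group, three-time mixed model, "Interaction terms will be used to assess the change in DBAS medication items".
- **H4** (Secondary Analysis Plan). Cognition and balance are analysed "using general linear mixed model (see Hypothesis 3 above"). The only effect size given is a worst case that assumes "no correlation between these measures at the two time points", for which "a post-test only analysis could detect a difference of" d=0.52.
- **H1b.** Days used has SD 1.94, with detectable effects of 0.60 days at r=0.83 and 0.70 days at r=0.77. A fallback that sets aside the recent study's data is 1.02 days (d=.53). Quantity of use has one figure, d=.53. Neither d=.53 comes with an analysis or a correlation.

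**The concern.** An interaction that leaves baseline means free in each arm compares change scores. When the baseline to follow-up correlation is low, subtracting baseline adds noise. With equal SDs and r below 0.5, the change comparison is less precise than ignoring baseline altogether, and less precise still than adjusting for it. The plan's ISI correlation is in that range.

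The same fact undermines the H4 figure. Zero correlation is a mild case for a post-test comparison but a bad one for an interaction, so a post-test d cannot be the floor for the interaction model. If the fitted model is the one H4 refers to, the secondary aim may be much less sensitive than stated. The H1b fallback and the only power figure for quantity of use raise the same question, because a reader cannot tell whether they apply to the planned model.

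**Working it through.** **Inputs.** From the Primary Analysis Plan: n=57 completers per arm (66 randomised), alpha 0.05 two-sided, power 0.80; ISI SD 5.3 with r=0.39 (0.24–0.52); days-used SD 1.94. The plan gives one SD per measure, so equal SDs at baseline and follow-up are an assumption, varied below through k = baseline SD / follow-up SD.

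**Variance of the between-arm contrast, in follow-up SD units:**
- post-test only: 2/57
- interaction, 57 complete pairs: 2(1 + k² − 2rk)/57
- interaction, all 66 baselines and 57 follow-ups per arm: 2[(1 − r²)/57 + (r − k)²/66]
- baseline-adjusted, or baseline means constrained equal: 2(1 − r²)/57, which does not involve k

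The detectable effect is 2.826 × SD × √variance (noncentral t, 112 df). The normal approximation uses 2.80. Ranges for the interaction run from the 66-baseline form to the complete-pairs form.

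**The plan's figures.**
- H2, r=0.39, complete pairs: √(2 × 1.22/57) = 0.2069; 2.826 × 5.3 × 0.2069 = 3.10, as stated. At r=0.24 the normal approximation gives 3.43, as stated. Both match a change-score variance, so the planned interaction leaves baseline means free.
- H4, post-test only: √(2/57) = 0.1873; d = 0.525 (normal) or 0.529 (t), matching 0.52.
- H1b: 0.60 days at r=0.83 and 0.69–0.70 at r=0.77, as stated.

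**H2, planned against adjusted (k=1).**

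| r | Planned | Adjusted | Power at 4.0 units, planned | Adjusted |
|---|---|---|---|---|
| 0.24 | 3.37–3.46 | 2.72 | 90–91% | 98% |
| 0.39 | 3.03–3.10 | 2.58 | 95–96% | 99% |
| 0.52 | 2.70–2.75 | 2.40 | 98–99% | >99% |

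At r=0.39 the variance ratio is 0.04103/0.02975 = 1.38 to 0.04281/0.02975 = 1.44. To match adjustment with 57 completers, the interaction would need 57 × 1.379 = 78.6 to 57 × 1.439 = 82.0 per arm. Power at 3.1 units is 80–82% planned and 92% adjusted. A post-test-only comparison would detect 2.81, so the planned test does worse than not using baseline ISI.

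The listed covariates do not close the gap. Entered as main effects, they are constant over time and drop out of a within-person change contrast when data are complete.

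SD sensitivity at r=0.39, follow-up SD held at 5.3: with k=0.8 planned is 2.80–2.83 (ratio 1.17–1.20); with k=1.25 it is 3.42–3.53 (1.75–1.87). Adjusted stays 2.58.

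For DBAS at r=0.55 the ratio is 1.25–1.29. For days used at r=0.83 it is 1.08–1.09.

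**H4, interaction (k=1).** The r=0.24 and 0.39 rows borrow the ISI values for illustration only.

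| r | Detectable d | Power at d=0.52 |
|---|---|---|
| 0 | 0.72–0.75 | 49–52% |
| 0.24 | 0.64–0.65 | 61–63% |
| 0.39 | 0.57–0.59 | 70–72% |
| 0.5 | 0.52–0.53 | 79–80% |

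The correlation at which the interaction reaches d=0.52 is 0.50–0.52 with equal SDs, 0.41–0.42 at k=0.8 and 0.62–0.64 at k=1.25.

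**H1b.** Post-test only gives 1.02 days (normal) or 1.03 (t). The interaction at r=0.5 gives 1.01–1.03 days, and at r=0 it gives 1.40–1.45. For the planned model, 1.02 days (1.02/1.94 = d 0.526) therefore needs r of 0.49–0.51, and d=.53 needs 0.48–0.50.

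**The case against.** On H2, nothing in the plan fails. The test is valid, the figures are right for it, the lower confidence limit of r is covered, and power at 4.0 units is 90% or better throughout. The choice between change and adjustment is partly preference, and the size of the gain depends on an SD ratio the documents do not give; at k=0.6 the variance ratio is only 1.04–1.05. The plan also never states a parameterisation, so free baseline means is an inference. All of this stands. The inference is nonetheless well supported, because the plan's own figures reproduce only with change-score variance, and adjustment is at least as precise at every k examined.

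On H4, the plan openly labels d=0.52 as post-test-only, the number is right for that analysis, and the secondary aim reads like a comparison at follow-up. The interaction enters only by cross-reference, and at r=0.6 it would detect about d=0.47, better than stated. So no actual shortfall is shown. But the label does not cure the mismatch: the specified model is the H3 one, its test is the interaction, and the quoted worst case is not that model's worst case.

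On H1b, the only correlation given for days used is 0.83 (lower limit 0.77), well above 0.5. What stands is that the fallback sets that study's data aside, and quantity of use has no correlation at all.

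**Conclusion.** The concern holds, with different weight for each part.

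- **H4** is the part that is wrong as written. The stated floor of d=0.52 is for an analysis other than the specified one. At zero correlation the specified interaction needs d=0.72–0.75 and has about 50% power at 0.52. It meets the stated figure only with r of about 0.5 or more (equal SDs), and the documents give no correlation for the cognition or balance measures.
- **H2** is an avoidable loss of efficiency, not an error: 3.03–3.10 against 2.58 ISI units at r=0.39, equivalent to about 79–82 completers per arm instead of 57. This rests on equal SDs at both times and on the unconstrained reading of the interaction.
- **H1b** is a limited point. For the planned model, 1.02 days and d=.53 hold only if r is about 0.5 or more, and the plan does not say what they assume.

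**What to change.** Keep the mixed models, but constrain the baseline mean to be equal in both arms, or adjust for the baseline value of the same outcome. Then:

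- **H2:** restate the detectable ISI effect as about 2.6 units (2.7 at r=0.24).
- **H4:** under the constrained model, about d=0.53 holds at r=0 with 57 tested per arm. If the unconstrained interaction is kept, give d=0.72–0.75 at r=0, or state the correlation assumed. For one-leg balance, base the figure on the number actually tested, because the VVC/Telephone Baseline Visit Procedures omit that test. The constrained model is preferable there, since a baseline covariate would drop participants without a baseline value.
- **H1b:** state the analysis and correlation behind 1.02 days and the quantity-of-use d=.53, or use the constrained model, under which about d=0.53 in follow-up SD units holds at any r.
- **H3:** if the DBAS figure is restated, note that r=0.55 is for the DBAS-16 and not the medication items being tested.

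The cost is a sentence of SAP wording, a small change in model specification, one restated ISI figure, one corrected H4 figure and one stated assumption for H1b. No new data are needed for H2. The one added assumption, equal baseline means, follows from randomisation.

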# Secondary Analysis Plan (H4)

[figure not shown]
We will test whether MTcap improves cognition (DSS, Symbol Copy; Trails A & B) and balance (One-leg balance) at post-treatment and 6-month follow-up, using general linear mixed model (see Hypothesis 3 above). Effect size calculations: For the most pessimistic case—no correlation between these measures at the two time points—a post-test only analysis could detect a difference of *d*=0.52.

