# VVC/Telephone Baseline Visit Procedures

Staff will conduct the 2 baseline assessment visits by VVC/telephone following the same protocol as used during in-person visits, except that the 1-leg balance test will not be performed. Certain items needed for the baseline assessment will be mailed to participants prior to the second baseline visit. These items include:

- Wrist actigraph
- 7-day sleep diary
- Hypnotic medication log
- Paper copies of the Trails, Digit Symbol/Symbol Copy tests
- Sleep apnea screening device (e.g., Watch PAT), if STOP-BANG score > 4
- Postage-paid, pre-addressed, insured delivery box ("Return Delivery" Box)

Participants will also have the option to meet staff at a VA GLAHS facility that is near their home to pick-up and return study devices//materials. In those circumstances, staff will meet the participant in a parking lot or lobby to exchange devices, while maintaining social distancing.

If it is determined that the MINI needs to be administered to a participant, a separate VVC visit will be scheduled.

| Table 2: Data Collection Instruments  |                               |   |   | Time point for data collection |      |          |  |
|---|-------------------------------|---|---|--------------------------------|------|----------|--|
| Instrument NAME   | Standard or
Study-Specific | Purpose   |   | Intervention                   | Post | 6-months |  |
|   | Standard                      | Self-reported   |   |                                |      |          |  |
| Self-Administered Comorbidity  Questionnaire                                     |                               |   | X |                                |      |          |  |
| Insomnia Severity Index (ISI)    | Standard                      | Insomnia symptoms severity  |   | Х                              | Х    | Х        |  |
| Pittsburgh Sleep Quality Index (PSQI)    | Standard                      | Self-reported sleep quality   |   | X                              | Х    | Х        |  |
| Dysfunctional Beliefs and Attitudes about Sleep – 16 item (DBAS-16)              | Standard                      | Beliefs about insomnia  |   |                                | Х    | Х        |  |

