| Alcohol, Smoking and Substance
Involvement Screening Test
(ASSIST)         | Standard                      | Screens for substance abuse   |   |                                |      |          |  |
| Trails A & B tests   | Standard                      | Mental processing speed, attention, executive functioning   | Х |                                | Х    | Х        |  |
| Digit Symbol Substitution and Symbol Copy                                        | Standard                      | Mental processing speed and attention   | Х |                                | Х    | Х        |  |
| Mini-Mental State Examination (MMSE)   | Standard                      | Cognitive status  | Х |                                | Х    | Х        |  |
| One-leg standing balance   | Standard                      | Balance measurement   | Х |                                | Х    | Х        |  |
| Benzodiazepine Dependence Questionnaire (DBEP)35  | Standard                      | Symptoms of benzodiazepine dependence   | Х |                                | Х    | Х        |  |
| Clinical Institute Withdrawal
Assessment Scale –
Benzodiazepines (CIWA-B)  | Standard                      | Symptoms of benzodiazepine withdrawal   | x | x                              | х    | х        |  |
| Credibility/expectancy
questionnaire (CEQ)                                    | Standard                      | Self-reported confidence in treatment   | × | Х                              | X    | ×        |  |
| Demographic questions   | Study-specific (attached)     | Characteristics of participants (e.g., marital status, living location, employment)   | х |                                |      |          |  |

| Fall event question                  | Study-specific (attached) | History of slips/trips/falls   | Х |   | Х | Х |
|--------------------------------------|---------------------------|--|---|---|---|---|
| ICSD-3 questions                     | Study-specific (attached) | Symptoms of insomnia based on ICSD-3 criteria  | Х |   | Х | Х |
| Additional comorbidity questions     | Study-specific (attached) | Self-reported medical/psychological conditions                                       |   |   |   |   |
| Nighttime urinary symptoms questions | Study-specific (attached) | Frequency and impact of nighttime urination  | Х |   | Х | Х |

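### Does omitting the one-leg balance test at remote baseline visits undermine H4's d=0.52 for balance?

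*Combined protocol and SAP*

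**What the plan says.** The Secondary Analysis Plan (H4) tests cognition "and balance (One-leg balance) at post-treatment and 6-month follow-up, using general linear mixed model (see Hypothesis 3 above". Its power statement assumes no correlation between time points and says that "a post-test only analysis could detect a difference of" d=0.52. The figure is given once for all measures.

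The H3 model it points to, in the Primary Analysis Plan, is a two-group by three-time mixed model: "Interaction terms will be used to assess the change in DBAS medication items". The same section fixes the numbers: 132 randomised and 13% expected to "fail to complete assessments", "yielding N=114 participants with complete data", or about 57 per arm.

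The telehealth text came later. Under VVC/Telephone Baseline Visit Procedures, remote baselines follow the in-person protocol "except that the 1-leg balance test will not be performed", while "Paper copies of the Trails, Digit Symbol/Symbol Copy tests" are mailed out. Table 2 lists "One-leg standing balance" at baseline, post-treatment and 6 months with no exception by visit mode. The telehealth and telephone text on follow-up neither includes nor excludes the test.

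**The concern.** Balance is one of the two domains of the secondary aim. Telehealth treats the domains differently at baseline: paper cognitive tests can be posted, whereas the one-leg test is dropped. The Potential Risks and Safety Plan has staff place a gait belt on the participant, which suggests that the test is impractical over video or telephone at follow-up too. Remote visits may be common: video use depends on VA guidance and participant preference, and Veterans from Loma Linda are to be seen by telehealth.

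A figure that needs every expected completer to be tested would then overstate the sensitivity for balance. Assessors at remote follow-up might also be unsure whether to attempt the test. In addition, the model named for H4 measures change from baseline, so absent baselines cost precision even where follow-up is complete.

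**Working it through.** **Inputs.** Two-sided alpha 0.05, power 0.80, 132 randomised 1:1 and 13% drop-out are from the Primary Analysis Plan and Randomization. Zero correlation and d=0.52 are from H4. The documents give no remote share and no correlation for balance. Both are assumed below, with shares equal by arm and no UCLA data.

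**1. The plan's own figure.** 132 × 0.87 = 114.84, taken as 114, or 57 per arm. For a post-test-only comparison, d = (1.960 + 0.842) × √(2/n):

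- n = 57: 2.8016 × √(2/57) = 0.525 (0.529 with the t distribution).
- Power at d = 0.52: 79% by either method.

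The stated 0.52 is therefore right to rounding. Baseline values do not enter this formula, so omitting the test at remote baseline leaves the figure unchanged.

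**2. If follow-up balance were also missing.** This is the same comparison with n = 57 × (1 − share), solved with the t distribution:

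| Share untested at follow-up (assumed) | n per arm | Detectable d | Power at d = 0.52 |
|---|---|---|---|
| 0% | 57 | 0.529 | 79% |
| 10% | 51.3 | 0.558 | 74% |
| 25% | 42.75 | 0.613 | 66% |
| 50% | 28.5 | 0.755 | 49% |

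Returning to 57 would take 57 − n further participants per arm with a follow-up balance result: about 6, 14 or 29.

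**3. If only baselines are missing, under the change contrast.** With n = 57 followed per arm and nb of them having a baseline, the variance per arm in SD units is (1−r)²/n + (1−r²)/nb, and d = 2.8016 × √(2 × variance).

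Check against H3 with nb = 57: r = 0.55 gives 0.498 and r = 0.39 gives 0.580. H3 states 0.50 and 0.58, so this is the contrast behind H3's power.

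Example at r = 0.5 with 25% missing: 0.25/57 + 0.75/42.75 = 0.02193, and 2.8016 × √0.04386 = 0.587.

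| Assumed r | 0% missing | 10% | 25% | 50% |
|---|---|---|---|---|
| 0.3 | 0.621 | 0.643 | 0.685 | 0.798 |
| 0.5 | 0.525 | 0.546 | 0.587 | 0.694 |
| 0.7 | 0.406 | 0.425 | 0.460 | 0.553 |

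At r = 0.5, power at d = 0.52 is 79%, 76%, 70% and 56% across the row. At r = 0.7, the detectable effect stays below 0.52 even with 25% missing.

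**4. How much of this is due to telehealth.** At r = 0.3 the complete-data contrast already exceeds the post-test figure by 0.621 − 0.525 = 0.096. Losing 25% of baselines adds 0.685 − 0.621 = 0.064. At r = 0 with complete data the contrast gives 0.742. The larger part of the gap is the difference between a post-test comparison and a change contrast. That difference has nothing to do with visit mode, and H4 says openly which of the two it reports.

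**5. Bias.** Baseline visit mode is settled before randomisation, so missing baselines can differ between arms only by chance. In a group-by-time model, baseline is one of three outcome occasions. A participant without it still contributes post-treatment and 6-month values and is not dropped.

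**The case for a change.** The best case for a change is that the documents do conflict on their face. Table 2 schedules the test everywhere, the remote baseline text removes it, and the safety precaution presumes staff are in the room. An assessor at a remote follow-up gets no direct instruction. Balance is also the dependent variable in the exploratory mediation analysis (E2), which inherits any gap. A footnote would cost little.

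Part of this stands: the documents do not say, by visit mode, whether the test is done at follow-up. The rest is weaker.

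- The remote baseline text is a specific exception to a general schedule, and the specific text governs. Where the authors meant to drop the test, they said so.
- The silence at remote follow-up is not particular to balance. Those sections do not mention the Trails or Digit Symbol tests either, so silence alone cannot show that balance is omitted while cognition is kept.
- The Setting section lets staff meet participants for baseline and follow-up assessments if needed, so a remote participant is not necessarily untested.
- The amendment at the end of the Exploratory Analysis Plan says the same analyses will be run with UCLA Health data added. Its size is unstated, but it works in the opposite direction to the loss.

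It is also true that 0.52 is not the detectable effect for the change contrast at zero correlation. That is a separate matter, independent of telehealth, and it alters no planned test.

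**Conclusion.** No change to the plan follows. H4's d=0.52 is correct for what it says it is: a post-test-only comparison at about 57 tested per arm. The one explicit telehealth change for balance, at baseline, does not touch it.

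The figure would be optimistic for balance only if follow-up tests were also missed. The loss is small at an assumed 10% (0.56) and material at 50% (0.76). Which of these applies, if any, cannot be known from the documents. Under the planned change contrast, missing baselines cost precision by an amount that depends on an unstated correlation.

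This is a secondary outcome on which the trial was not sized. A revised detectable effect would rest on an assumed share and an assumed correlation, and it would change no estimate, model or decision. What is left is missing operational detail that staff and analysts can fill sensibly: test where staff are present, analyse the balance data obtained, and report the number tested. The confidence interval for balance will then show the precision achieved. This conclusion assumes that missed follow-up balance tests, if any, arise from visit mode and not from treatment arm.
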